6.3.2 Treatment blinding

Participants, investigator staff, and persons performing the assessments, will remain blinded to the identity of the treatment from the time of randomization until final database lock. Since the primary analysis is planned when all participants have completed the 12-week randomized, double-blind, placebo-controlled period, Novartis study team members will be blinded from time of randomization until the primary analysis database lock. The study side site pharmacist/nurse or other designated qualified site personnel who prepares the study drug and the unblinded CRA will remain unblinded.

Unblinding a single participant at site for safety reasons (necessary for participant management) will occur via an emergency system in place at the site. As a result, the unblinded participant should be discontinued from the study treatment.

The following methods will be used to maintain the blind:

- Randomization data will be kept strictly confidential until database lock for the primary analysis and will not be accessible by anyone else involved in the study with the following exceptions:
 - an independent analysis team that needs to prepare safety and efficacy interim and safety monitoring analysis reports for the DMC,
 - unblinded pharmacist/purse or other designated qualified site personnel at study site
 - unblinded pharmacist/nurse or other designated qualified site personnel at study site and unblinded CRA monitoring the sites.

These personnel will not be involved in any other trial activities.

2. The identity of the treatments will be concealed by the use of study treatment that are all identical in packaging, labeling, schedule of administration, appearance, and odor. All

XXB750/matching placebo injections will be prepared such that they will all have the same injection volumes regardless of dose to maintain the blinding. Blinded label supply (also mention respective drug name) will be provided at sites to the unblinded site pharmacist or other designated qualified site personnel in order to prepare study drug and to conceal treatment code from participants and the investigator staff administering the study injections/dispending the study medications and performing the assessments.

At the time of safety review/interim analysis for design adaptation, the DMC will review unblinded safety/interim reports created by an independent analysis team. More details about the DMC review process and how unblinding data will be handled in the context of DMC reviews will be provided in the DMC charter.

Table 6-3 provides an overview of various key study personnel and their extent of unblinding.

Table 6-3 Blinding and unblinding plan

Role	Time or Event				Ι
Kole	Randomization list generated	Treatment allocation & dosing	Safety event (single subject unblinded)	Interim Analysis/ dose escalation/ safety review conducted by DMC	Primary analysis
Participants	В	В	В	В	В
Site Staff	В	В	В	В	В
Unblinded site staff, e.g. pharmacy staff	В	UI	В	В	В
Global Clinical Supply	UG	UG	UG	UG	UI
Randomization Office	UI	UI	UI	UI	UI
Unblinded Sponsor staff, e.g. for study treatment re-supply,	UG	UG	UG	UG	UI
Unblinded Pharmacovigilance Sponsor staff	В	В	UI	В	UI
Independent committees used for assessing interim results, if required (e.g. DMC)	UI	UI	UI	UI	UI
Independent Statistician/statistical programmer/ data analysts (e.g. unblinded monitor(s)	UI	UI	UI	UI	UI
Sponsor CTT	В	В	В	В	UI

Role	Time or Event				
	Randomization list generated	Treatment allocation & dosing	Safety event (single subject unblinded)	Interim Analysis/ dose escalation/ safety review conducted by DMC	Primary analysis
All other Sponsor staff not identified above (i.e. project team, management & decision boards, support functions)	В	В	UI	В	UI

B Complete blinded

UG Unblinded at the group level (i.e has access to unblinded group level summary results, but not to the individual participant treatment codes)

UI Unblinded to individual participant treatment codes

6.3.3 Emergency breaking of assigned treatment code

Emergency code breaks must only be undertaken when it is required to in order to treat the participant safely.

Most often, discontinuation from study treatment and knowledge of the possible treatment assignments are sufficient to treat a study participant who presents with an emergency condition. Emergency treatment code breaks are performed using the IRT. When the Investigator contacts the system to break a treatment code for a participant, he/she must provide the requested participant identifying information and confirm the necessity to break the treatment code for the participant. The Investigator will then receive details of the investigational drug treatment for the specified participant and a fax or email confirming this information. The system will automatically inform the Novartis monitor for the site and the study team that the code has been broken.

It is the Investigator's responsibility to ensure that there is a dependable procedure in place to allow access to the IRT at any time in case of emergency. The Investigator will provide:

- protocol number
- participant number

In addition, oral and written information to the participant must be provided on how to contact his/her backup in cases of emergency, or when he/she is unavailable, to ensure that un-blinding can be performed at any time.

In case of emergency unblinding, the participant should be discontinued from study treatment and continue with the study visits as scheduled without study medication administration.

6.4 Study treatment compliance

The investigator must promote adherence to treatment by instructing the participant to take the antihypertensive background therapy exactly as prescribed and by stating that compliance is necessary for the participant's safety and the validity of the study results. This information

should be captured in the source document at each visit. All administered study treatment must be recorded in the Drug Accountability Log.

Injections of XXB750/matching placebo will be administered at the site. Study medication administration and compliance information must be captured in the source document, the appropriate CRF/s and in the Drug Accountability Log.

Adherence to the background antihypertensive therapy medications may be evaluated using urine drug screen by LCMS at end of run-in and Week 12 (EOT) post-randomization.

6.4.1 Recommended treatment of potential anticipated adverse events

described Recommendations for handling hypertension and hypotension are in Section 6.5.3 and Section 10.7, respectively.

Recommendations for handling Liver events are described in Section 10.5.1

Recommendations for handling potential drug induced liver injury (DILI) cases are described in Section 6.5.4.1

Recommendations for handling Renal events are described in Section 10.6.1

Medication used to treat adverse events (AEs) must be recorded on the appropriate CRF.

6.5 Dose modification

6.5.1 Dose escalation guidelines

Participants randomized into XXB750 dose level 4, will start at dose level 3 and will be up titrated at the Visit 130 (week 4 visit) to dose level 4.

Starting dose 6.5.1.1

Participants will be randomized to XXB750 dose level 1, dose level 2, dose level 3, dose level 4 or matching placebo. Participants randomized to XXB750 dose level 4 will start at dose level 3 and will be force up-titrated to dose level 4 at Visit 130 (week 4 visit).

Provisional dose levels 6.5.1.2

Table 6-4 XXB750 dose levels evaluated during this trial

Dose levels	Monthly dose	Increment from previous dose
1	30 mg	NA
2	60 mg	100%
3	120 mg	100%
4	240 mg	100%

6.5.2 Definitions of dose limiting toxicities (DLTs)

Not Applicable

6.5.3 Dose modifications

Except for force up-titration of study medications outlined in Section 6.5.1.1, Investigational study treatment dose adjustments and/or interruptions are not permitted. Participants who are considered to be intolerant to study medications should discontinue study treatment.

Safety criteria determining dose interruption or discontinuation based on liver or renal events are listed in Appendix 5 (Section 10.5) and Appendix 6 (Section 10.6), respectively. Deviations from mandatory dose interruptions and/or reductions are not allowed.

If the participant experiences severe hypertension (defined as SBP > 180 mmHg confirmed by 3 readings 5 minutes apart), consider discontinuing all study medication and starting the subject on open label treatment accompanied by monitoring of BP as per local standard of care until the doses of the new medications are stable and BP is under control.

Dose modifications of background therapy

Dose adjustments of any component(s) of the background antihypertensive therapy medications and study medication due to hypotension are listed in Section 10.7.

6.5.4 Follow-up for toxicities

Refer to Appendix 5 (Section 10.5) for the follow-up of liver events and Appendix 6 (Section 10.6) for the follow-up of renal events.

6.5.4.1 Follow up on potential drug-induced liver injury (DILI) cases

Transaminase increases combined with total bilirubin increases may be indicative of potentially severe DILI and should be considered as clinically important events and assessed appropriately to establish the diagnosis. The required clinical information, as detailed below, should be sought to obtain the medical diagnosis of the most likely cause of the observed laboratory abnormalities.

The threshold for potential DILI may depend on the participant's baseline AST/ALT and total bilirubin value; participants meeting any of the following criteria will require further follow-up as outlined below:

- For participants with normal ALT and AST and total bilirubin value at baseline: AST or ALT > 3.0 x ULN combined with total bilirubin > 2.0 x ULN
- For participants with elevated AST or ALT or total bilirubin value at baseline: [AST or ALT > 2 x baseline level] OR [AST or ALT > 300 U/L] (whichever occurs first) combined with [total bilirubin > 2 x baseline level AND > 2.0 x ULN]

As DILI is essentially a diagnosis of exclusion, other causes of abnormal liver tests should be considered and their role clarified before DILI is assumed to be the cause of liver injury.

A detailed history, including relevant information such as review of ethanol consumption, concomitant medications, herbal remedies, supplement consumption, history of any pre-existing liver conditions or risk factors, should be collected.

Laboratory tests should include ALT, AST, total bilirubin, direct and indirect bilirubin, Gamma-glutamyl transferase (GGT), prothrombin time (PT)/ International normalized ratio

(INR), alkaline phosphatase, albumin, and creatine kinase. If available, testing of Glutamate Dehydrogenase (GLDH) is additionally recommended. Refer to Section 10.5.1 for further guidance.

Perform relevant examinations (Ultrasound or MRI, Endoscopic retrograde cholangiopancreatography [ERCP]) as appropriate, to rule out an extrahepatic cause of cholestasis.

Table 6-5. provides guidance on specific clinical and diagnostic assessments which can be performed to rule out possible alternative causes of observed liver function test (LFT) abnormalities.

Table 6-5 Diagnostic assessments to determine alternative causes of observed LFT abnormalities

Disease	Assessment
Hepatitis A, B, C, E	IgM anti-HAV; HBsAg, IgM & IgG anti-HBc, HBV DNA; anti-HCV, HCV RNA, IgM & IgG anti-HEV, HEV RNA
CMV, HSV, EBV infection	IgM & IgG anti-CMV, IgM & IgG anti-HSV; IgM & IgG anti-EBV
Autoimmune hepatitis	Antinuclear Antibodies (ANA) & Anti-Smooth Muscle Antibody (ASMA) titers, total IgM, IgG, IgE, IgA
Alcoholic hepatitis	Ethanol history, GGT, MCV, CD-transferrin
Nonalcoholic steatohepatitis	Ultrasound or MRI
Hypoxic/ischemic hepatopathy	Medical history: acute or chronic congestive heart failure, hypotension, hypoxia, hepatic venous occlusion. Ultrasound or MRI.
Biliary tract disease	Ultrasound or MRI, ERCP as appropriate.
Wilson disease (if <40 yrs old)	Cæruloplasmin
Hemochromatosis	Ferritin, transferrin
Alpha-1-antitrypsin deficiency	Alpha-1-antitrypsin

MCV: mean corpuscular volume; ERCP: Endoscopic retrograde cholangiopancreatography; HAV: hepatitis A virus; HBV: hepatitis B virus; HCV: hepatitis C virus; HEV: hepatitis E virus; CMV: cytomegalovirus; EBV: Epstein Barr virus; CD-transferrin: carbohydrate-deficient transferrin; MRI: magnetic resonance imaging; HBsAg: Hepatitis B virus surface antigen; HSV: Herpes simplex virus

Other causes should also be considered based upon participants' medical history such as hyperthyroidism (causing thyrotoxic hepatitis where T3, T4, thyroid-stimulating hormone [TSH] should be tested), CV disease (causing ischemic hepatitis where an ECG could be performed, and the history of prior hypotensive episodes should be inquired), and Type 1 diabetes mellitus (causing glycogenic hepatitis).

Following the appropriate causality assessments, as outlined above, the causality of the treatment is estimated as "probable" (i.e. >50% likely), if it appears greater than all other possible causes of liver injury combined. The term "treatment-induced" indicates probably caused by the treatment, not by something else, and only such a case can be considered a DILI case and should be reported as an SAE.

All cases confirmed on repeat testing meeting the laboratory criteria defined above, with no other alternative cause for LFT abnormalities identified, should be considered as "medically significant" and thus, meet the definition of SAE and should be reported as a SAE using the term "potential treatment-induced liver injury." All events should be followed-up with the outcome clearly documented.

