Treatment-emergent elevations in AST or ALT (>3x ULN) in combination with total bilirubin >2x ULN or jaundice in the absence of cholestasis (defined as ALP < 2 ULN) or other causes of hyperbilirubinemia can be an indicator of severe drug induced liver injury (Hy's Law). For this reason, a potential Hy's Law case requires expedited reporting, and will be handled as a serious unexpected adverse event (assessing it as medically significant in the absence of any other seriousness criteria). It must be reported as an SAE to the sponsor promptly (i.e., even before all other possible causes of liver injury have been excluded). Reporting should include all available information, especially that needed for evaluating the diagnosis, severity and likelihood that the study treatment caused the reaction. For patient monitoring and to better understand potential etiologies, the investigator must initiate a close follow-up until complete resolution of the problem and completion of all attempts to obtain supplementary data.

All new malignant neoplasms will be assessed as serious under "medically significant" if other seriousness criteria are not met.

All reports of intentional misuse and abuse of the product are also considered serious adverse events irrespective of whether a clinical event has occurred.

Any suspected transmission via a medicinal product of an infectious agent is also considered a serious adverse reaction.

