10.5 Appendix 5: Liver safety monitoring

10.5.1 Liver event and laboratory trigger definitions & follow-up requirements

Table 10-3 Liver event and laboratory trigger definitions

	Definition/ threshold
If ALT or AST normal at baseline	
Liver laboratory triggers	· 3 x ULN < ALT or AST ≤ 5 x ULN
	· TBL > ULN*
Liver events	· ALT or AST > 5 × ULN
	· ALP > 2 × ULN (in the absence of known bone
	pathology)
	· Total bilirubin > 3 × ULN (in the absence of known Gilbert syndrome)
	· ALT or AST > 3 × ULN AND (TBL > 2 x ULN OR INR >
	1.5)
	· Potential Hy's Law cases (defined as ALT or AST > 3
	× ULN and Total bilirubin > 2 × ULN [mainly conjugated
	fraction] without notable increase in ALP to > 2 ×
	ULN)†
	· Any clinical event of jaundice (or equivalent term) · ALT or AST > 3 × ULN accompanied by (general)
	malaise, fatigue, abdominal pain, nausea, or vomiting,
	or rash with eosinophilia
	· Any adverse event potentially indicative of a liver
	toxicity
If ALT or AST elevated at baseline:	
Liver laboratory triggers	· ALT or AST > 2 x baseline or > 200 U/L (whichever
	occurs first) · TBL > ULN*
Liver events	· ALT or AST > 3 x baseline or > 300 U/L (whichever
Liver events	occurs first)
	· (ALT or AST > 2 × baseline or > 200 U/L [whichever
	occurs first]) AND (TBL > 2 x ULN OR INR > 1.5)
	\cdot ALT or AST > 5 × ULN
	· ALP > 2 × ULN (in the absence of known bone
	pathology)
	· Total bilirubin > 3 × ULN (in the absence of known Gilbert syndrome)
	· Potential Hy's Law cases (defined as ALT or AST > 3
	× ULN and Total bilirubin > 2 × ULN [mainly conjugated
	fraction] without notable increase in ALP to > 2 × ULN)
	· Any clinical event of jaundice (or equivalent term)
	· (ALT or AST > 2 × baseline or > 200 U/L [whichever
	occurs first]) accompanied by (general) malaise, fatigue, abdominal pain, nausea, or vomiting, or rash
	with eosinophilia
	· Any adverse event potentially indicative of a liver
	toxicity
* Fractionate bilirubin, evaluate for cholestation	c liver injury (ALP) or alternative causes of bilirubin elevation. Treat

^{*} Fractionate bilirubin, evaluate for cholestatic liver injury (ALP) or alternative causes of bilirubin elevation. Treat alternative causes according to local institutional guidelines

[†] Please, consult Section 8.6.2 on reporting requirements of potential Hy's Law cases

Table 10-4 Follow-up requirements for liver triggers (based on ALT, AST and TBL values)

values)				
	ALT	TBL	Liver Symptoms	Action
ALT increase without bilirubin increase:				

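### For potential Hy's Law cases that also meet its laboratory criteria, Protocol 6.5.4.1 makes the SAE report wait on causality or repeat confirmation, while 8.6.2 wants it before other causes are excluded

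*Protocol*

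**What the plan says.** **Protocol 6.5.4.1** defines the cases it covers by laboratory values. If ALT, AST and bilirubin were all normal at baseline, the criterion is "AST or ALT > 3.0 x ULN combined with total bilirubin > 2.0 x ULN". If any of the three was elevated, it is AST or ALT above twice baseline or above 300 U/L, "combined with [total bilirubin > 2 x baseline level AND > 2.0 x ULN". Two sentences then deal with SAE reporting:

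- After the causality assessment, a case is treatment-induced if treatment is more than 50% likely to be the cause, and "only such a case can be considered a DILI case and should be reported as an SAE".
- Cases that meet the laboratory criteria, are confirmed on repeat testing and are "with no other alternative cause for LFT abnormalities identified" count as medically significant and are reported as SAEs.

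**Protocol 8.6.2** covers AST or ALT above 3 x ULN with bilirubin above 2 x ULN or jaundice, "in the absence of cholestasis (defined as ALP < 2 ULN) or other causes of hyperbilirubinemia". It states that "a potential Hy's Law case requires expedited reporting" and that the SAE report goes to the sponsor promptly, "even before all other possible causes of liver injury have been excluded". It does not split by baseline. Table 10-3 likewise lists potential Hy's Law cases in the block headed "If ALT or AST elevated at baseline" as well as in the normal-baseline block.

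**Protocol 8.6.3** sets a 24-hour limit from awareness for any SAE and lets later information go in as follow-up. Sections 6.4.1 and 8.4.6.1 send sites to 6.5.4.1 for handling potential DILI.

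**The concern.** One participant can fall under two rules that disagree on when, and on what condition, an SAE report is due. Section 6.5.4.1 is the section named for potential DILI. It does not cite 8.6.2 or say that the report comes first, and the word *only* in its first reporting sentence reads as a restriction.

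A site that works from 6.5.4.1 alone could hold the report until the work-up is finished. If it finds a competing cause, it might file no SAE under this rule unless another seriousness criterion, such as hospitalization, applies. Laboratory values and adverse events would still reach the database, and SAP Table 2-4 tabulates the Hy's Law combination from laboratory data. What is at stake is therefore expedited notice to the sponsor, not the safety tables built from laboratory values. That notice matters here: Section 4.2 describes the available safety data as limited, and Section 4.1 says the drug may be detectable for about 90 days after the last dose.

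**Working it through.** The documents give no figure to reproduce. The check compares thresholds and clocks.

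**1. Which cases fall under both sections?** Let *b* be the baseline of one enzyme in multiples of its ULN, and *U* that ULN in U/L. The documents give no ULN, so 30 to 55 U/L is assumed for ALT.

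- 8.6.2 trigger: 3 x ULN.
- 6.5.4.1 trigger, normal baseline tests: 3 x ULN.
- 6.5.4.1 trigger, elevated baseline: min(2*b*, 300/*U*).

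Exclusion criterion 17 allows AST/ALT up to 3 x ULN at Visit 1, so elevated-baseline participants can be enrolled.

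| Baseline of that enzyme (x ULN) | 6.5.4.1 trigger | 8.6.2 trigger | Values under one section only |
|---|---|---|---|
| all tests normal | 3.0 | 3.0 | none |
| 1.2 | 2.4 | 3.0 | 2.4-3.0, 6.5.4.1 only |
| 1.5 | 3.0 | 3.0 | none |
| 2.0 | 4.0 | 3.0 | 3.0-4.0, 8.6.2 only |
| 2.5 | 5.0 | 3.0 | 3.0-5.0, 8.6.2 only |
| 3.0 | 5.45-6.0 | 3.0 | 3.0 up to 5.45-6.0, 8.6.2 only |

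The last row is 2 x 3.0 = 6.0, or 300/55 = 5.45 at a ULN of 55 U/L.

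Bilirubin: with normal baseline tests both sections use 2 x ULN. With an elevated baseline bilirubin, 6.5.4.1 needs twice baseline. At 1.5 mg/dl, the Visit 1 limit, and an assumed ULN of 1.0 to 1.3 mg/dl, that is 2 x 1.5/1.3 = 2.3 to 2 x 1.5/1.0 = 3.0 x ULN, against 2 x ULN in 8.6.2.

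Results:

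- Normal baseline, non-cholestatic, bilirubin above 2 x ULN: full overlap.
- Elevated baseline: partial overlap. ALT rising from 2.0 to 4.1 x ULN, with bilirubin above both 2 x baseline and 2 x ULN, is under both sections.
- ALT rising from 2.0 to 3.5 x ULN, with AST below its own trigger and bilirubin above 2 x ULN, is under 8.6.2 only.
- 8.6.2 cases identified by jaundice with bilirubin not above 2 x ULN are outside 6.5.4.1.

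For a single enzyme, 2*b* >= 3 once *b* >= 1.5, so a value above twice baseline also exceeds 3 x ULN. This fails across enzymes. With baseline ALT 1.6 and AST 0.6 x ULN, an AST of 1.3 exceeds 2 x 0.6 = 1.2, so it meets the 6.5.4.1 transaminase rule far below 3 x ULN.

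**2. Do the reporting conditions conflict?** 8.6.2 expressly waives the exclusion of other causes. Both sentences in 6.5.4.1 depend on assessing other causes: one through the 50% judgement, the other through finding no alternative. That is a direct conflict. That the report should also precede repeat confirmation is an inference from the word *promptly* and the 24-hour limit.

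**3. How late could a report be?** Table 10-4 puts the repeat panel at 48-72 hours. Start both clocks at the first result and suppose the site waits for that panel: 48 - 24 = 24 hours late, 72 - 24 = 48 hours late. A repeat within 24 hours costs nothing on this step. The cause work-up adds time that the documents do not quantify.

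**4. Would the sponsor's laboratory alerts catch the case?** With a normal baseline, Table 10-2 alerts start above 5 x ULN for AST/ALT and above 3 x ULN for bilirubin. ALT at 4 x ULN with bilirubin at 2.5 x ULN meets the 8.6.2 values but triggers neither alert.

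**The case against.** The SAE rule is stated where SAE rules belong. Section 8.6.2 is mandatory in tone, while 6.5.4.1 is a follow-up section that uses *should*, and its first reporting sentence can be read as defining a final DILI classification. The Amendment 2 summary records wording added to 8.6.2 to alert investigators and a footnote added to Table 10-3, so the sponsor's intention is clear. Sites can reach 8.6.2 through Appendix 5 and 8.4.6.1. A site that reports first and sends the work-up as follow-up satisfies both sections. Participant protection does not depend on SAE status either: as extracted, Table 10-4 has study drug interrupted for ALT above 3 x ULN with bilirubin above 2 x ULN, and restarted only if another cause is found and enzymes return to baseline.

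All of this stands, and it limits the consequence. It does not reconcile the two texts. Sections 6.4.1 and 8.4.6.1 direct sites to 6.5.4.1, which gives a later and narrower reporting rule without pointing to 8.6.2. In the extracted text the Table 10-3 footnote mark sits only on the normal-baseline Hy's Law row, although this may be an artefact of reading the PDF.

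A reader might infer that 6.5.4.1 holds back reporting of every potential Hy's Law case, whatever the baseline. The documents do not support that. Its reporting sentences are written for cases meeting its own criteria, and some elevated-baseline cases under 8.6.2 do not meet them. For those the issue is a mismatch of thresholds. Nor does 6.5.4.1 forbid earlier reporting.

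**Conclusion.** The point holds for potential Hy's Law cases that also meet the 6.5.4.1 laboratory criteria: all non-cholestatic normal-baseline cases with AST/ALT above 3 x ULN and bilirubin above 2 x ULN, and those elevated-baseline cases that also meet the baseline-multiple or 300 U/L criteria. For these, following 6.5.4.1 alone does not satisfy 8.6.2.

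The possible harm is a late SAE report, or none under this rule if a competing cause is identified. The 24-48 hour figure is conditional on a site treating the repeat panel as its gate for reporting; the documents do not say that sites will do so. They give no expected number of cases, which is likely small with about 170 participants. The normal-baseline overlap needs no assumed ULN; the upper ends of the elevated-baseline bands do. The text should be corrected because expedited reporting is a firm duty and the partial safeguards do not replace it. No efficacy analysis is affected.

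**What to change.** Let 8.6.2 govern reporting. In 6.5.4.1, replace the conditional SAE wording with:

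> Any case meeting the potential Hy's Law criteria of Section 8.6.2, regardless of baseline liver values, is reported as an SAE within 24 hours of awareness per Sections 8.6.2 and 8.6.3; repeat tests and the causality assessment are submitted as follow-up.

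Keep the 50% test only for final DILI classification. Keep the repeat-confirmation sentence only for cases that meet 6.5.4.1 but not 8.6.2, such as a cholestatic case or an elevated-baseline case above twice baseline but not above 3 x ULN. Add a direct cross-reference to 8.6.2, and put the Table 10-3 footnote on the elevated-baseline Hy's Law row if it is not already there.

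The cost is a text change made through a written amendment with the approvals that Section 10.1.8.1 requires (sponsor, IRB/IEC, and health authorities where applicable), plus a notice to sites. No new data, visits or analyses are needed.

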8.6.3 SAE reporting

To ensure participant safety, every SAE, regardless of causality, occurring after the participant has provided informed consent and until End of Study visit must be reported to Novartis safety immediately, without undue delay, but under no circumstances later than within 24 hours of obtaining knowledge of the events. (Note: If more stringent, local regulations regarding reporting timelines prevail). Detailed instructions regarding the submission process and requirements are to be found in the Investigator folder provided to each site. Information about all SAEs is collected and recorded on the eSAE (electronic Serious Adverse Event) with paper backup (as further detailed in the CRF Completion Guideline). Serious Adverse Event Report Form: all applicable sections of the form must be completed in order to provide a clinically thorough report. SAE reported after the EOS visit must be collected and reported to Novartis using the paper SAE form provided to the site.

Screen failures

SAEs occurring after the participant has provided informed consent until the time the participant is deemed a Screen Failure must be reported to Novartis.

Run-in or Baseline failures

SAEs collected between the time the participant has provided informed consent until time that participant is determined to be a run-in failure or a baseline failure must be reported to Novartis.

Randomized participants

SAEs occurring between the time the participant has provided informed consent until either EOS visit or until 3 months after the last dose of injectable study drug (whichever is longer) must be reported to Novartis. Any SAE experienced by participants who discontinue study treatment prematurely but remain in the study for follow-up, should continue to be reported until either EOS visit or until 3 months after the last dose of injectable study drug (whichever is longer).

All follow-up information for the SAE including information on complications, progression of the initial SAE and recurrent episodes must be reported as follow-up to the original episode immediately, without undue delay, but under no circumstances later than within 24 hours of the Investigator receiving the follow-up information (Note: If more stringent, local regulations regarding reporting timelines prevail). An SAE occurring at a different time interval or otherwise considered completely unrelated to a previously reported one must be reported separately as a new event.

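### Protocol 6.5.4.1 makes SAE reporting of liver injury wait for a causality judgement or a repeat test, while 8.6.2 requires potential Hy's Law cases to be reported promptly, before other causes are excluded

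*Protocol*

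**What the plan says.** Section 6.5.4.1 gives two routes by which a liver case becomes an SAE.

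- **Causality route.** After the causality assessments, treatment counts as the probable cause if it is more than 50% likely. Of a case that passes this test, the section says "only such a case can be considered a DILI case and should be reported as an SAE".
- **Confirmation route.** The next paragraph makes SAEs of "All cases confirmed on repeat testing meeting the laboratory criteria defined above, with no other alternative cause for LFT abnormalities identified".

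Section 8.6.2 covers potential Hy's Law cases. It describes them as "Treatment-emergent elevations in AST or ALT (>3x ULN) in combination with total bilirubin >2x ULN or jaundice in the absence of cholestasis" or other causes of hyperbilirubinemia, and then says: "It must be reported as an SAE to the sponsor promptly (i.e., even before all other possible causes of liver injury have been excluded".

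Section 8.6.3 sets the general rule. It applies to "every SAE, regardless of causality", and reporting must be immediate and "under no circumstances later than within 24 hours of obtaining knowledge of the events".

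**The concern.** Section 6.5.4.1 puts the SAE report at the end of the work-up, and 8.6.2 puts it at the start. Section 6.4.1 sends sites to 6.5.4.1 for handling potential drug-induced liver injury, so a site facing a combined transaminase and bilirubin rise would naturally open that section. The two SAE paragraphs there do not mention the earlier duty.

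What is at stake is expedited reporting of the liver signal that the protocol itself treats as a possible marker of severe injury. Section 4.2 says that only limited safety data exist for this antibody. Late or absent reports would delay what the sponsor sees.

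**Working it through.** The plan gives no figure to reproduce. The check is whether the same participant can fall under both instructions, and what each one then requires.

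**Step 1: do the populations overlap?** The limits for a participant with normal ALT, AST and bilirubin at baseline are:

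| | 6.5.4.1 | 8.6.2 |
|---|---|---|
| AST or ALT | > 3.0 x ULN | > 3 x ULN |
| Total bilirubin | > 2.0 x ULN | > 2 x ULN, or jaundice |
| Cholestasis | not a condition | absent (ALP < 2 x ULN) |

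The transaminase and bilirubin limits are identical. Every normal-baseline case that meets the 8.6.2 laboratory limits therefore also meets those of 6.5.4.1.

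**Step 2: what must have happened before the SAE report?**

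| | 6.5.4.1, causality route | 6.5.4.1, confirmation route | 8.6.2 with 8.6.3 |
|---|---|---|---|
| Repeat test | not stated | required | not required |
| Causality judged > 50% | required | not required | not required |
| Other causes excluded | treatment must outweigh them all combined | none identified | expressly not awaited |
| Time limit | none stated | none stated | 24 hours from knowledge |

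**Step 3: one illustrative participant.** Assume a normal baseline, then ALT 4 x ULN, bilirubin 2.5 x ULN, ALP below 2 x ULN and no other cause known on the day of the result. Since 4 > 3 and 2.5 > 2, both sections apply.

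- *No other cause is ever found.* Under 8.6.2 and 8.6.3 the report is due within 24 hours of the result being known. Under 6.5.4.1 read alone, it follows the repeat test or the causality judgement. The report is late.
- *The work-up later points to another cause.* Under 8.6.2 the report was already due. Under 6.5.4.1 read alone, neither route is met, because treatment is not the probable cause and an alternative has been identified. Unless another seriousness criterion applies, the report is missed.

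**Step 4: which rule is intended?** The Amendment 2 list says that wording was put into 8.6.2, with a footnote to Table 10-3, to alert investigators to SAE reporting of liver injury. That supports 8.6.2 as the governing rule, and it is used here only as a guide to intent.

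**The case against.** **The cross-references already lead to 8.6.2.** Section 6.5.4 points to Appendix 5, 6.5.4.1 points to 10.5.1 for further guidance, and a Table 10-3 footnote points to 8.6.2 for reporting potential Hy's Law cases. This stands, and it lowers the risk. It does not remove a sentence in 6.5.4.1 that gives a different reporting condition. In the available text the footnote mark sits only on the normal-baseline Hy's Law entry, though a mark may have been lost from the other.

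**The sections deal with different things.** On this view 6.5.4.1 says when a case may finally be called DILI, and 8.6.2 says when a suspected case is reported. The confirmation route also shows that the word only in 6.5.4.1 is not an exclusive SAE test. Reporting first and classifying later is a workable reading, but 6.5.4.1 does not state it. Its sentence ties the label and the report together, and the confirmation route also depends on follow-up being finished.

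**A stronger reading on limits.** The limits "For participants with elevated AST or ALT or total bilirubin value at baseline" include "AST or ALT > 2 x baseline level] OR [AST or ALT > 300 U/L] (whichever occurs first) combined with" bilirubin above both 2 x baseline and 2 x ULN. A reader might infer that Hy's Law cases escape through these limits. The arithmetic is right. With ALT going from 2.5 to 4.75 x ULN and bilirubin from 0.8 to 2.5 x ULN, 4.75 > 3 and 2.5 > 2. Yet 4.75 is below 2 x 2.5 = 5.0, and at an assumed ALT ULN of up to 55 U/L it is at most 4.75 x 55 = 261 U/L, below 300. The documents do not support a lost case, for three reasons:

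- Section 8.6.2 gives SAE status whatever the baseline.
- Section 8.4.6.1 already sends Table 10-3 events to the 6.5.4.1 work-up.
- Section 6.5.4.1 announces that its threshold may depend on baseline.

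**A stronger reading on timing.** A reader might set the 48-72 hour panel of Table 10-4 against the 24-hour limit and infer a fixed delay. Section 6.5.4.1 gives no interval for its repeat test. The inference also needs a site that disregards both 8.6.2 and 8.6.3.

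**Conclusion.** The contradiction is real and should be corrected. It is limited to the SAE wording of 6.5.4.1 set against 8.6.2 and 8.6.3, and it arises at any baseline for a case that meets both sets of limits.

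The consequence is a risk, not a certainty: late or missed expedited reporting of potential Hy's Law cases by a site working from 6.5.4.1. Section 8.6.2 still binds every site. The documents give no expected number of such cases; that it is small is a judgement.

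Dose interruption follows Appendix 5 and is untouched. No efficacy analysis is affected. The liver categories in SAP Table 2-4 count participants on central laboratory values, so a case that meets the limits there is counted whether or not an SAE was filed.

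**What to change.** Change only the SAE wording in 6.5.4.1:

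1. Keep the part of the sentence that reserves the DILI label for probably treatment-induced cases, and remove the reporting condition attached to it.
2. State that any case judged probably treatment-induced is still reported as an SAE.
3. Add: *Potential Hy's Law cases, whatever the baseline, are reported as SAEs per Section 8.6.2 within the Section 8.6.3 timeline, before repeat testing or causality assessment is complete; the causality assessment follows.*
4. Keep the sentence that makes other confirmed cases SAEs, so that no case loses that status.

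The laboratory limits in 6.5.4.1 need no change.

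The cost is a written protocol amendment, with sponsor, ethics committee and, where required, health authority approval under 10.1.8.1. No new tests are needed. A few early SAE reports will later be attributed to another cause, but 8.6.2 already requires those reports.
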